## 4.3 Benefit/Risk

Subjects in clinical trials generally cannot expect to receive direct benefit from treatment during participation, as clinical trials are designed to provide information about the safety and effectiveness of an investigational medicine.

Because the primary objective of this study is to evaluate the efficacy in parallel study under double-blind, in order to wash-off the prior medication's effect, subject is not allow to use lipid lowering agents 8 weeks prior to randomization (Visit 3) and see the values of lipid panels during treatment period. On the other hand, since there is no placebo arm during treatment period, subject is assigned to active arm only.

Additional details regarding specific benefits and risks for subjects participating in this clinical trial may be found in the accompanying Investigators Brochure (IB) and Informed Consent documents.

Protocol/Amendment No.: 832-01

#### 5.0 METHODOLOGY

# **5.1** Entry Criteria

# 5.1.1 Diagnosis/Condition for Entry into the Trial

Male/Female subjects with hypercholesterolemia between the ages of 20 and 80 years (inclusive) will be enrolled in this trial.

Subjects with screening one value/finding outside the range described in the inclusion or exclusion criteria may, at the discretion of the investigator, have one repeat determination performed and if the repeat value satisfies the criterion, they may continue in the screening process. Only one specific out of range value/finding should be repeated (not entire panel).

# 5.1.2 Subject Inclusion Criteria

In order to be eligible for participation in this trial, the subject must:

<Visit 1: Screening, Week  $-8 \sim -3 >$ 

- 1. Japanese male or female and between  $\geq 20$  and  $\leq 80$  years of age on the day of signing informed consent.
- 2. Subject understands the study procedures alternative treatments available, and risks involved with the study, and voluntarily agrees to participate by giving written informed consent.
- 3. Outpatient with hypercholesterolemia.
- 4. Subject is a male or female subject who is of reproductive potential agrees about contraception, or a female subject who is not of reproductive potential.

Female subject who is of reproductive potential has to agree to remain abstinent or use (or partner use) two acceptable methods of birth control from date of signed informed consent to the 14 days after the last dose of study drug. Acceptable methods of birth control are: intrauterine device (IUD), diaphragm with spermicide, condom, and vasectomy.

A female subject who is not of reproductive potential is eligible without requiring the use of contraception. A female subject who is not of reproductive potential is defined as: one who has either 1) reached natural menopause defined as age 46 or older with 12 months of spontaneous amenorrhea, 2) 6 weeks post surgical bilateral oophorectomy or hysterectomy, or 3) bilateral tubal ligation.

5. Subject will maintain a stable diet that is consistent with the Japan Atherosclerosis Society Guideline 2012 (JAS 2012) for prevention of atherosclerotic cardiovascular diseases for the duration of the study.

<Visit 2: Placebo run-in, Week -2>

- 6. Subject has TG value < 400 mg/dL at Visit 1.
- 7. Subject has CK (CPK) value  $\leq 3$  x upper limit of normal (ULN) [per central laboratory reference ranges] at Visit 1.

04ROM Confidential

**Protocol/Amendment No.:** 832-01

8. Subject has ALT and AST value  $\leq 2$  x ULN [per central laboratory reference ranges] at Visit 1.

## < Visit 3: Randomization>

9. Subject meets any of the following criteria.

Category will be assessed based on Section 12.3. (JAS2012).

LDL-C value will be calculated by Friedewald method at Visit 2.

Friedewald method: LDL-C = Total cholesterol – HDL-cho – TG/5.

- (1) Subject is categorized "Category I" and has LDL-C value ≥160 mg/dL to <220 mg/dL
- (2) Subject is categorized "Category II" and has LDL-C value ≥140 mg/dL to <190 mg/dL
- (3) Subject is categorized "Category III" and has LDL-C value  $\geq$ 120 mg/dL to <160 mg/dL
- 10. Subject able to follow the instruction for drug administration and is greater than 75% compliant with study medication during the single-blind placebo run-in period.

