# 2.0 TRIAL DESIGN

# 2.1 Trial Design

This is a Randomized, active-controlled, parallel-group, multi- site, double-blind trial of MK-0653H in subjects with hypercholesterolemia to be conducted in conformance with Good Clinical Practices.

**Protocol/Amendment No.:** 832-01

The study consists of a screening period, a placebo run-in period, a treatment period, and follow up, and the total duration of each subject is 17 to 22 weeks, depending on the length of the screening period, which is according to subjects' prior lipid-lowering therapy. For subjects on lipid-lowering therapy, this screening period will be 6 weeks and during this period, subject washoff prior lipid lowering therapy. In patients on a lipid lowering therapy (ie., statin) at Visit 1, investigators should consider the patients LDL-C level on the statin to assess whether the patient is likely to qualify for entry at Visit 2 after the wash-out of statin therapy. For subjects not on lipid-lowering therapy, it will be 1-6 weeks depending on the state of prior pharmacotherapy other than lipid-lowering agents in each subject. Subjects who meet all of the eligibility criteria will be enrolled in 12 weeks of treatment period following a 2-week placebo run-in period. Subjects will be randomized to one of the 5 treatment groups [Ezetimibe monotherapy at 10 mg, Rosuvastatin calcium (hereafter Rosuvastatin or Ros) monotherapy at 2.5 mg or 5 mg, MK-0653H (EZ 10 mg + Ros 2.5 mg), or MK-0653H (EZ 10 mg + Ros 5 mg)] in an allocation ratio of 1:2:2:2:2. Three hundreds six subjects will be randomized to ensure 279 completers. Subjects will be centrally randomized using an Interactive Voice/Web Response System (IVRS/IWRS). Subjects who complete the study or prematurely discontinue during the study will receive a 14-day follow-up phone call to assess for serious adverse events.

Specific procedures to be performed during the trial, as well as their prescribed times and associated visit windows, are outlined in the Trial Flow Chart - Section 6.0. Details of each procedure are provided in Section 7.0 – Trial Procedures.

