# 6.0 TRIAL FLOW CHART

Phase	Screening (1~6 weeks)	Placebo run-in (2 weeks)	Treatment (12 weeks)		Follow up		
Week	Week -8~ -3¹	Week -2	Week 0	Week 4	Week 8	Week 12/ Discontinuati on	14 days after last dosing
Visit number	Visit 1	Visit 2	Visit 3	Visit 4	Visit 5	Visit 6	
Visit window permitted (Day) 	N/A	7~42+7	14+/-3	28+/-7	28+/-7	28+/-7	
Administrative procedure	1						
Obtain Informed Consent 	X						
Collect Medical History	X						
Review Inclusion/Exclusion criteria	X	X	X				
Review Prior/Concomitant Therapies	X	X	X	X	X	X	
Contact Patient Registration Center	X	X	X	X	X	X	
Risk assessment 	X	X	X				
Review Diet/Exercise and Instruct on JAS Guidelines	X						
Monitor Dietary/Exercise Compliance		X	X	X	X	X	
Dispense Study Drug 		X	X	X	X		
Randomized (assignment of randomization number)			X				
Monitor Medication compliance/patient diary			X	X	X	X	
Safety assessment							15
Review adverse event	X	X	X	X	X	X	X 15
Perform Physical Examination 		X				X	
Vital sign  Height/Weight 	X		X			X	
Sitting Blood Pressure/Pulse	X	X	X	X	X	X	
ECG		X					
Laboratory test 							
Lipid Panel A 	X	X	X	X	X	X	
hs CRP			X			X	
Apo protein (Apo) B			X	X	X	X	
Blood Chemistry 	X	X	X	X	X	X	
Hematology 	X					X	
TSH	X						
HbA1 C 	X					X	
Urinalysis 	X		X			X	
Pregnancy test 	X	X	X	X	X	X	

**Protocol/Amendment No.:** 832-01

1. Interval between Visit 1 and Visit 2 is determined depending on the presence of the prior treatments. Subjects washing out lipid-lowering therapy will have Visit 1 at -6 weeks from Visit 2; subjects not requiring washout will have Visit 1 at -1~-6 weeks from Visit 2 depending on the state of prior pharmacotherapy other than lipid-lowering agents in each subject.

- 2. Visit window is relative to previous Visit.
- 3. Informed consent must be obtained before any protocol-related study procedures are performed. It is allowable to obtain informed consent before Visit 1. After obtaining informed consent, subject will be given a unique screening number (refer to 7.1.1.6) and a subject identification card (refer to 7.1.1.3).
- 4. Subject's risk category assessment is determined at Visit 3 according to the Japan Atherosclerosis Society (JAS) Guideline 2012 based on the results obtained at Visit 1 and 2 (refer to Appendix 12.3).

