# 7.1.3.1 Laboratory Safety Evaluations (Hematology, Chemistry and Urinalysis)

Laboratory tests for hematology, chemistry and urinalysis are specified in Table 3.

Table 3 Laboratory Tests

Category	Test
Lipid Panel A	LDL-C, total cholesterol (TC), HDL-C, non-HDL-C, and Triglyceride (TG)
hs-CRP	
Apo protein (Apo) B	
Blood Chemistry	Glucose, ALT, AST, ALP, uric acid, total bilirubin, BUN, CK (CPK), creatinine, Cl, potassium, sodium, γ-glutamyl transferase
Hematology	hemoglobin, platelet count, red blood cell count, white blood cell count, hematocrit
TSH	
HbA1 C	NOTE: Subjects who have diagnosed with diabetes only
Urinalysis	pH, glucose (qualitative), protein (qualitative)
Pregnancy test	Urine pregnancy test (urine hCG) will be determined at the site.
	Serum $\beta$ -hCG test is determined by central lab if urine pregnancy performed is positive.
	NOTE: female subjects who have reproductive potential Only

Laboratory safety tests will be performed after at least a 10-hour fast.

Fasting blood samples will be drawn as outlined in the Study Flow Chart. The central laboratory will perform all laboratory test determinations. LDL-C will be calculated using the Friedewald method when TG≤400 mg/dL and beta quantification ultracentrifugation when TG>400 mg/dL. All Lipid Panel A, Apo B and hs-CRP data will be blinded once the subject is centrally randomized. Once a subject is randomized (Visit 3), no attempts should be made on the part of the investigator or subject to have a local evaluation of the subject's lipid values (Lipid Panel A, Apo B and hs-CRP).

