## **7.1.5.1** Screening (Visit 1)

Potential subjects will be evaluated to determine that they fulfill the entry requirements as set forth in Section 5.1. A signed informed consent will be obtained prior to performing any protocol study procedures.

Screening procedures may be repeated after consultation with the Sponsor. In case of rescreening, all procedure listed at screening visit including informed consent should be performed.

Screening visit will be performed 1 to 6 weeks prior to Visit 2. Subject must discontinue the prior medication (except probucol) for hypercholesterolemia [fish oils, CholestinTM, bile acid sequestrants, statins, Ezetimibe, fibrates or niacin (>200 mg/day)] at least 6 weeks prior to Visit 2. If subject has taken probucol, probucol must be discontinued from at least 10 weeks prior to Visit 2. If a subject is eligible for study participation, a 10 hour fasting blood sample will be drawn.

Subject will be instructed on the JAS2012 diet and exercise, and will agree to maintain the diet/exercise regimen throughout the study.

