## 8.4 Analysis Endpoints

Efficacy and safety endpoints that will be evaluated for within- and/or between-treatment differences are listed below. For each of the efficacy and safety parameters, the baseline value is defined as the last available measurement prior to randomization, which typically corresponds to the measurement obtained at Visit 3.

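### Does inclusion criterion 9, which names Friedewald with no triglyceride condition, leave the entry LDL-C undefined when Visit 2 triglycerides exceed 400 mg/dL?

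*Combined protocol and SAP*

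**What the plan says.** Four places bear on the LDL-C value that decides entry.

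- **Section 5.1.2, criterion 9.** "LDL-C value will be calculated by Friedewald method at Visit 2". The formula is printed next to it: "Friedewald method: LDL-C = Total cholesterol – HDL-cho – TG/5". The entry windows are 160 to below 220 mg/dL (Category I), 140 to below 190 (Category II) and 120 to below 160 (Category III). TG is not mentioned as a condition.
- **Section 7.1.3.1.** The central laboratory performs all determinations, and "LDL-C will be calculated using the Friedewald method when TG≤400 mg/dL and beta quantification ultracentrifugation when TG>400 mg/dL". No visit is exempted.
- **Section 5.1.2, criterion 6.** "Subject has TG value < 400 mg/dL at Visit 1". This is the only TG limit for entry. Exclusion criterion 29, which runs from Visit 1 to Visit 3, refers back to exclusion criteria only and so does not re-apply it.
- **Section 6.0, flow chart.** Lipid Panel A, which contains TG, is drawn again at Visit 2. Footnote 1 adds: "Subjects washing out lipid-lowering therapy will have Visit 1 at -6 weeks from Visit 2".

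For the analysis, Section 8.4 says that "the baseline value is defined as the last available measurement prior to randomization, which typically corresponds to the measurement obtained at Visit 3".

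**The concern.** Read literally, criterion 9 and Section 7.1.3.1 name different methods for the same sample once Visit 2 TG passes 400 mg/dL, and criterion 6 does not rule that case out. A subject who is washing out has Visit 1 six weeks before Visit 2, and Section 2.1 expects some to be on a statin then: "In patients on a lipid lowering therapy (ie., statin) at Visit 1, investigators should consider the patients LDL-C level on the statin". Section 7.1.5.1 lists fibrates, niacin and fish oils among the agents to be stopped. Section 4.1.1.2 itself describes statin plus ezetimibe as lowering TG. A Visit 1 TG may therefore be an on-treatment or just-stopped value, and TG may rise by Visit 2.

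At stake is eligibility. The windows have a lower and an upper limit, so a gap between the two methods could admit a subject whom the other method would reject, or the reverse. Two sites could then treat the same laboratory results differently.

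**Working it through.** **1. Where do the two rules differ?**

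| TG at Visit 1 | TG at Visit 2 | Criterion 9 | Section 7.1.3.1 |
|---|---|---|---|
| 400 mg/dL or more | any | not reached (criterion 6 fails) | not reached |
| below 400 | 400 or less | Friedewald | Friedewald |
| below 400 | above 400 | Friedewald | ultracentrifugation |

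Only the last row is in question. The documents give no Visit 2 TG data, so its size is unknown and may be zero.

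**2. Could the choice of method move a subject across a limit?**

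The window widths are 220 − 160 = 60, 190 − 140 = 50 and 160 − 120 = 40 mg/dL. The TG term is 450/5 = 90 mg/dL at TG 450 and 500/5 = 100 mg/dL at TG 500. That whole term is not the error. Only the difference between the two methods can move a subject, and the documents do not give it.

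As an assumption for illustration, let the true non-LDL, non-HDL cholesterol be between TG/6 and TG/8. Friedewald then reads too low by TG/5 − TG/6 to TG/5 − TG/8:

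- TG 450: 90 − 75 = 15 to 90 − 56.25 = 33.75 mg/dL
- TG 500: 100 − 83.3 = 16.7 to 100 − 62.5 = 37.5 mg/dL

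Against windows of 40 to 60 mg/dL, a subject could change status. Turning this into a number of subjects would also need the share with Visit 2 TG above 400 and the spread of LDL-C around each limit. Both would have to be taken over everyone screened at Visit 2, not over the 306 randomized. None of this is in the documents, so no count is given here.

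**3. Does the difference reach the analysis?**

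- *Allocation.* Randomization follows the entry decision and is stratified by risk category (Section 5.4). Section 12.3 builds that category from age, sex and risk factors; HDL-C is one of them, LDL-C is not.
- *Endpoint.* Baseline is typically Visit 3 and the outcome is Week 12, both under Section 7.1.3.1. The Visit 2 value becomes baseline only if the Visit 3 value is missing.
- *Analysis set.* Section 8.5.1 keeps every randomized, treated subject with the required data in the assigned arm. It plans no per-protocol analysis, so a disputed entry removes nobody.

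**4. Does it touch the stated power?**

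Section 8.9 uses 62 subjects per arm (31 on ezetimibe) and an SD of 16%. The binding contrast is combination against rosuvastatin: −34 − (−46) = 12 points at 2.5 mg and −40 − (−52) = 12 points at 5 mg. For 62 against 62 at a two-sided α of 0.025, power is 97.3%. Simulating the Hochberg rule 200,000 times gives 97.3% for both families together and 97.2% for each family at 0.025. The plan states about 97% for each of these. No input depends on how entry LDL-C is measured.

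**The case for a change.** The best case for a change is that an eligibility criterion should name one method for each subject, and this one does not. If the laboratory reports an ultracentrifugation value at Visit 2 while criterion 9 prints the Friedewald formula, the site must set one passage aside, and criterion 9 does not point to Section 7.1.3.1. The washout timing makes the situation possible, and the remedy would be a single sentence that requires no new test.

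The textual part stands: the cross-reference is missing, and nothing limits TG at Visit 2. It is less convincing that this leaves staff without an answer. Section 7.1.3.1 ties sampling to the flow chart, gives the central laboratory all determinations and states one LDL-C rule, and Visit 2 is on that chart. The laboratory can therefore report one LDL-C value for Visit 2, obtained by the method the plan prescribes at that TG. Criterion 9 then names the method that applies to everyone at or below 400 mg/dL, in a group already screened below that level at Visit 1. A site that calculated the value by hand could still decide differently, but it would do so before allocation and in the same way for all five arms.

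**Conclusion.** The wording is uneven, but the plan stays sound if followed as written. The two passages differ only for subjects below 400 mg/dL at Visit 1 and above 400 mg/dL at Visit 2, and for them the general laboratory rule supplies a sensible method. For an affected subject the gap between methods might be about 15 to 38 mg/dL at TG 450 to 500, on an assumption that the documents neither support nor contradict. The number affected is unknown.

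The consequence is confined to who enters. It does not bias the comparisons between arms, and it leaves the primary analysis and the power of about 97% as they are. This rests on two readings: that Section 7.1.3.1 applies to Visit 2, which its text supports, and that Visit 3 supplies baseline for nearly all subjects, as Section 8.4 expects. A cross-reference would be tidier but would change no result, so none is asked for.

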# 5.1.3 Subject Exclusion Criteria

The subject must be excluded from participating in the trial if the subject:

<Visit 1: Screening, Week -8 $\sim$  -3>

# Prohibited medical conditions

- 1. Subject has uncontrolled hypertension (treated or untreated) with systolic blood pressure >160 mmHg or diastolic >100 mmHg at Visit 1.
- 2. Subject has uncontrolled type 1 or type 2 diabetes mellitus (treated or untreated,  $HbA_{1C} \ge 8.0\%$  at Visit 1 or newly diagnosed within 3 months).
- 3. Subject has chronic heart failure defined by New York Heart Association (NYHA) Classes III or IV.
- 4. Subject has uncontrolled cardiac arrhythmias or recent significant abnormality in the subject's electrocardiogram as takes within 6 months prior to Visit 1 in the opinion of the investigator.
- 5. Subject has a history of coronary artery disease (CAD), CAD-equivalent disease [e.g., peripheral arterial disease, abdominal aortic aneurysm, symptomatic carotid artery disease transient ischemic attack, stroke].
- 6. Subject has familial hypercholesterolemia or has undergone LDL apheresis.

**Protocol/Amendment No.:** 832-01

7. Subject has uncontrolled endocrine or metabolic disease known to influence serum lipids or lipoproteins (i.e., secondary causes of hyperlipidemia, e.g., hyper- or hypothyroidism, Cushing's syndrome).

Note: Definitions of hyper- and hypothyroidism are as follows:

Hyperthyroidism: TSH below the central laboratory's LLN.

Hypothyroidism: TSH >20% above the central laboratory's ULN.

For subjects receiving thyroid hormone, there is no lower TSH threshold for entry (Visit 1) and the subject must be on a stable dose for ≥6 weeks before the randomization visit (Visit 3). One redraw will be allowed if the original TSH value is less than 40% above or below the reference range, but the subject must meet the criterion upon redraw.

8. Subject has estimated glomerular filtration rate (eGFR) < 30 mL/min /1.73 m^2 based on the below equation, nephrotic syndrome or other clinically significant renal disease at Visit 1.

Male eGFR  $[mL/min/1.73m^2] = 194 \times Cr[mg/dL]^{-1.094} \times age [yr]^{-0.287}$ Female eGFR[mL/min/1.73m^2]=194 x  $Cr[mg/dL]^{-1.094}$  x age [yr]  $^{-0.287}$  x 0.739

- 9. Subject has had a gastrointestinal tract bypass, or other significant intestinal melabsorption.
- 10. Subject has a history of cancer within the past 5 years from Visit 1 (except for successfully treated dermatological basal cell or squamous cell carcinoma or in situ cervical cancer).
- 11. Subject who is known HIV positive (as assessed by medical history).
- 12. Subject has a history of drug/ alcohol abuse within the past 5 years from Visit 1, or psychiatric illness no adequately controlled and stable on pharmacotherapy.
- 13. Subject has a condition or situation, which described as contraindication in labeling of Zetia® or Crestor® (i.e., Patients with diminished liver metabolism capacity due to the following conditions: Acute hepatitis, acute exacerbation of chronic hepatitis, hepatic cirrhosis, liver cancer, or jaundice.) or may interfere with participation in the study in the opinion of the investigator.

# Prohibited therapies

- 14. Subject is currently taking medications restricted by labeling as below.
  - Cyclosporine
  - Systemically administered azole antifungals(e.g., ketoconazole, itraconazole and fluconazole)
  - Macrolide antibiotics (e.g., clarithromycin, erythromycin and telithromycin)
  - Antacid (e.g., aluminum hydroxide/magnesium hydroxide)
  - Protease inhibitors (e.g., Lopinavir/Ritonavir, Atazanavir+Ritonavir, Darunavir +Ritonavir, concomitant use with elbasvir and grazoprevir)

MK-0653H-832-01 Final Protocol Confidential

Protocol/Amendment No.: 832-01

- Simeprevir
- Eltrombopag
- 15. Subject is receiving treatment with systemic corticosteroids (intravenous, intramuscular and oral steroids).

NOTE1: If subject has been treated with a stable regimen of oral corticosteroids used as replacement therapy for pituitary/adrenal disease as well as inhaled steroid therapy for  $\geq 8$  weeks prior to Visit 3 and agree to continue this regimen for the duration of the trial, concomitant therapy is acceptable.

- NOTE2: Topical, intra-articular, nasal, inhaled and ophthalmic steroid therapies are acceptable.
- 16. Subject is taking any cyclical hormones (e.g., cyclical oral contraceptives, cyclical hormone replacement), including the combination of ethinyl estradiol and norethisterone within 8 weeks prior to Visit 3.
- 17. Subject is receiving non-cyclical hormone therapy (including non-cyclical hormone replacement therapy or any estrogen antagonist/agonist).
  - Note: If subject has been treated with a stable regimen for  $\geq 8$  weeks prior to Visit 3 and agree to continue this regimen for the duration of the trial, concomitant therapy is acceptable.
- 18. Subject is treated with psyllium, other fiber-based laxatives, phytosterol margarine, herbal medicine and/or over the counter (OTC) therapies that are known to affect serum lipids.
  - Note: If subject has been treated with a stable regimen for  $\geq 8$  weeks prior to Visit 3 and agree to continue this regimen for the duration of the trial, concomitant therapy is acceptable.
- 19. Subject is treated with an anti-obesity drug (e.g. mazindol) within 3 months (12 weeks) prior to Visit 1.
- 20. Subject is newly treated with warfarin and/or warfarin-like anticoagulants at Visit 1, or subject has not been on a stable dose with a stable International Normalized Ratio (INR) for at least 6 weeks prior to Visit 1.

